For a particular environmental chamber trial, baseline data will be collected while resting in a thermoneutral environment outside of the environmental chamber. Participants will then enter the environmental chamber and be seated while instrumentation is completed. Subjects will then exercise at a mild/moderate workload for 60 min. The assigned cooling modality will be employed throughout the exercise bout. The primary assessed variables are the increase in internal and skin temperatures. Upon completion of the exercise bout, participants will rest for no more than 60 minutes in the chamber during which time we will monitor temperatures and obtain echocardiogram images, then the environmental temperature will be reduced and subjects will be de-instrumented.

Data will be digitized upon acquisition, name encrypted, and stored in password protected computer folders. Only approved personnel will have access to subject files that will otherwise be locked. Research data and medical history will be available to the PI and his staff. Members and staff of the Institutional Review Board (IRB) at UT Southwestern Medical Center and Texas Health Presbyterian Hospital may review subjects' records. A representative of these IRBs may contact the subject for information about their experience with this research project. The subject may refuse to answer any questions the representative of the IRB may ask. All subjects' information will be kept confidential unless the subject

Form A

IRB # 30204 | STU-2020-0334

gives the researchers permission to share with others or if the investigators are required by law to release it. All hard copy documents will be stored behind at least two locked doors/devices and only individuals who are involved in this research project can access the files. Information contained in reports or publications issued as a result of this research project will be presented in such a way that the subject identity will not be revealed. The signed consent form will be kept on file in the subject's laboratory chart. Disclosure of information to third parties will be prohibited.

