Statistical support will be provided by [name]., Professor in the Department of Clinical Sciences, Division of Biostatistics at UT Southwestern Medical Center at Dallas. Descriptive statistics (i.e., group characteristics such as age, body mass, BSA burned, physical activity questionnaire data, etc.) will be analyzed via one-way analysis of variance to compare the three study groups. Within each environmental exposure, the primary evaluation will address an expected interactive effect of group and the employed cooling condition (e.g., Conditions A-D as outlined in Table 1) on the magnitude of the elevation in internal body temperature to 60 min of exercise. These data will be statistically analyzed via a two-factor mixed-effects model repeated measures analysis with main factors of group and the applied cooling condition (crossover repeated factor), and their interaction, with subject modeled as a random effect and specifying covariance structure, using SAS Proc Mixed. Potential mechanisms contributing to differing elevations in internal body temperature (e.g., differences in magnitude of changes in skin temperature and skin surface water vapor pressure) as a result of the exercise bouts will be statistically evaluated via the same approach. The extent and significance of the expected interactions will be statistically explored post-hoc with appropriate comparisons derived from the models' least square means contrasts, applying Bonferroni type adjustments for multiple testing.

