We estimated power to detect a 0.5 °C mean difference in the elevation in internal body temperature to the exercise bout between groups. This number was obtained from one of our prior studies in which similar thermoregulatory responses to exercise in burn survivors were assessed, with a standard deviation of the elevation in internal body temperature being ~0.3 °C. Based upon these estimates, 12 subjects per group for each environmental exposure would provide omnibus power of 0.94 for group differences in the elevation in internal body temperature of 0.45 °C at an alpha of 0.05 and power of 0.84, using an adjusted alpha of 0.0125 to account for multiple comparison evaluations of the four interventions between groups. For the within group comparison, power is >0.9 to detect a difference in the increase in internal body temperature of 0.4 °C at an alpha of 0.0125 (power analyses from: NCSS PASS 15). Nevertheless, we will enroll 18 subjects per group (9 male and 9 female) for each environmental exposure to allow for attrition as well as provide additional power to evaluate any sex-related differences, should they become apparent. Randomization within groups for the order of the applied cooling modality will be implemented with a Latin square blocking design.

Form A

IRB # 30204 | STU-2020-0334

4.b. List of the study intervention(s) being tested or evaluated under this protocol

	N/A - this study does not test or evaluate an intervention. Skip to item 4.d.		
#	Study intervention(s) being tested or evaluated under the protocol Add or delete rows as needed	Affiliate Place a check next to institution(s) where the intervention will be performed	Local Standard Practice? Indicate whether the intervention is considered acceptable practice locally for applicable institutions
1	Skin cooling (fan and skin wetting)	 UTSW	 Yes
		 PHHS	 Yes
		 CMC	 Yes
		 THR	 Yes
		 TSRH	 Yes
		 Other: _____	 Yes

4.c. Risk:Benefit Analysis of study interventions being tested or evaluated under this protocol

For each study intervention identified in section 6b above, complete a risk:benefit analysis table.

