a. Describe the procedures for protecting against or minimizing any potential risks for each of the more than minimal risk research procedures listed above.

Exercise in the prescribed climate conditions: Internal body temperature will be monitored throughout each experiment. The protocol will stop, and the environmental temperature will be reduced, in the unlikely occurrence that internal body temperature exceeds 39.5°C or upon any indication of adverse cardiovascular or neurological symptoms (e.g., lightheadedness, hypotension, hypertension, nausea, etc. Our experiences are that the burn survivors and non-burned control subjects tolerate the exercise bout well. Upon completion of each protocol, we will ensure that each subject is normothermic and adequately hydrated prior to being permitted to leave the laboratory.

Peripheral intravenous catheter and blood samples: There is a small risk of infection and a still smaller risk of a blood clot or breakage of the catheter. The likelihood of these complications is remote (less than 1 in 10,000) when the procedure is carried out by trained personnel and proper equipment is used, as during this study. There is also a small risk of the catheter perforating the vein or not being inserted into a blood vessel. The participant may have discomfort, bleeding, and/or bruising and on rare occasions, a person may feel dizzy or faint.

Body composition (DXA): The radiation exposure from this procedure is negligible and is estimated to be 0.06 mR, which is equivalent to 1/286th the dose of a standard chest x-ray and less than a day's exposure to natural radiation.

Sweat gland activation with iodine embedded paper: This procedure will not be performed if a participant has a known allergy to iodine. Given the very small amount of iodine embedded in the paper, even if the participant is unknowingly allergic to iodine, this exposure is unlikely to cause any irritation; an exception could be a minor rash if the person is particularly sensitive.

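### The primary model uses each chamber visit's starting internal temperature only by subtraction; a within-subject covariate might sharpen the cooling contrasts and the interaction

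*Combined protocol and SAP*

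**What the plan says.** Section 4.a (Research Plan), statistical analysis paragraph, makes the primary evaluation the interaction of group and cooling condition "on the magnitude of the elevation in internal body temperature to 60 min of exercise". The SAS Proc Mixed model has "main factors of group and the applied cooling condition (crossover repeated factor), and their interaction, with subject modeled as a random effect". Neither this paragraph nor any other part of the document names starting temperature as a covariate.

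The starting value should be on hand for every analysed trial:
- The trial procedures in section 4.a state that "baseline data will be collected while resting in a thermoneutral environment outside of the environmental chamber".
- Table 2 in section 3 schedules internal temperature at Visits 2 to 5, the four chamber visits, but not at screening Visit 1.
- Section 5.a states: "Internal body temperature will be monitored throughout each experiment". The procedures table in section 4.d lists it as continuous.

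The power paragraph in section 4.a also works on the change alone, "with a standard deviation of the elevation in internal body temperature being ~0.3 °C".

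**The concern.** The elevation is final minus starting temperature. Analysing it without a covariate assumes that a visit which begins 0.1 °C warmer also ends 0.1 °C warmer. The random subject effect removes stable differences between people, but not a person's variation in starting temperature from one visit to the next. If that variation does not carry through one for one to the end of exercise, part of it stays in the change score as noise.

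That noise falls on the within-subject comparisons: the cooling contrasts and the group by condition interaction, which is the primary test. At stake is efficiency. The plan collects a value that might reduce this noise and does not use it for that purpose.

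**Working it through.** **1. The plan's own power figures.** Inputs from the power paragraph: 12 per group, SD 0.3 °C, difference 0.45 °C, alpha 0.05 and 0.0125 (two-sided assumed). For a pairwise contrast with error pooled over three groups (33 df), the standard error is 0.3 × √(2/12) = 0.1225 and the noncentrality is 0.45/0.1225 = 3.67. Power is 0.946 and 0.842, against the stated 0.94 and 0.84. The figures reproduce without any covariate.

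**2. What subtraction leaves behind.** Let X be the start and Y the end, both as within-subject visit deviations, with SDs sX and sY and correlation r. The slope of Y on X is β = r·sY/sX. The slope of the change (Y − X) on X is b = β − 1. So variation in X enters the change with coefficient β − 1, and adjustment removes the fraction

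b²·sX² / Var(Y − X).

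This is zero when β = 1, that is, when r = sX/sY.

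**3. Size with the documented SD of the change.** The documents give 0.3 °C for the change, but not sX, r, or the correlation of changes across visits. Assume that last correlation is 0.5. The within-subject variance of the change is then 0.3² × 0.5 = 0.045. With b = −0.5 (assumed):

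| Visit-to-visit SD of start (assumed) | b²·sX² / 0.045 | Simulated variance ratio, adjusted/unadjusted |
|---|---|---|
| 0.10 °C | 0.0025/0.045 = 5.6% | 0.94 |
| 0.15 °C | 0.005625/0.045 = 12.5% | 0.89 |
| 0.20 °C | 0.0100/0.045 = 22.2% | 0.78 |

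The simulation used 3 groups of 12 subjects with 4 visits each, and includes the cost of estimating the slope. It gives cuts of about 6%, 11% and 22%.

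**4. Size if start and end have equal SDs.** The fraction in step 2 becomes (1 − r)/2: 25% at r = 0.5, 15% at 0.7 and 10% at 0.8. With unequal SDs it can vanish:
- sY/sX = 2, r = 0.5: β = 1, gain 0%.
- sY/sX = 1.5, r = 0.5: β = 0.75, gain 0.0625/1.75 = 3.6%.
- sY/sX = 1.25, r = 0.8: β = 1, gain 0%.

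**5. Cost if the covariate is uninformative.** With b = 0 the simulated variance ratio is about 1.01. The model has 3 × 11 × 3 = 99 within-subject residual degrees of freedom with 12 per group, and loses one.

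**6. Effect on group contrasts.** A subject's deviations from his or her own mean sum to zero over four complete visits. The term therefore leaves the group main-effect contrasts unchanged. A subject-mean term would not. If two groups differ by 0.2 °C in mean start and the between-subject slope of change on start is −0.5 (both assumed), the group contrast moves by 0.2 × 0.5 = 0.10 °C, for example from 0.30 to 0.40 °C.

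**7. Where precision could matter.** The power paragraph states within-group power above 0.9 for 0.4 °C at alpha 0.0125, without a within-subject correlation ρ. A paired t test with n = 12 and SD of the difference 0.3 × √(2(1 − ρ)) gives 0.925 at ρ = 0.5 (SD 0.300) and 0.767 at ρ = 0.25 (SD 0.367). In the second case a 15% variance cut, less one df, gives about 0.83.

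**The case against.** The strongest case for leaving the plan alone is this. Elevation is the declared outcome, and subtracting the start is already a correction for it. Condition order is randomised, so the unadjusted cooling contrasts are unbiased. The stated between-group power reproduces without adjustment at 12 per group, and 18 will be enrolled. All of that stands. It limits the point to efficiency but does not remove it.

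A reader might infer more, in four ways that the documents do not support:
- **All starting variation contaminates the change score.** It enters with coefficient β − 1. At r = 0.8 with equal SDs, that is one fifth of it.
- **The gain is small only if start and end are very highly correlated.** That holds for equal SDs only. Step 4 shows zero gain at r = 0.5 when the end SD is twice the start SD. The end value follows 60 minutes of exercise, so equal SDs cannot be taken for granted.
- **A 10% to 25% gain is the expected one.** With the within-subject change SD of 0.21 °C from step 3 (√0.045), the equal-SD rows imply a visit-to-visit SD of the start of 0.21 °C at r = 0.5, 0.27 °C at 0.7 and 0.34 °C at 0.8. No figure in the documents supports these.
- **Full baseline adjustment is harmless.** The burn and control groups are not randomised, so a subject-mean term changes what the group comparison estimates.

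Two practical points also stand. Resting baseline is taken outside the chamber and seated instrumentation follows inside, so the starting value must be defined. Section 5.a also allows an ingested pill, a rectal thermometer or a suppository pill. A constant offset between methods cancels in the deviation if a subject keeps one method for all four visits. A change of method between visits would add noise to the covariate.

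**Conclusion.** The point holds as a minor, optional improvement in precision. The primary model omits a value available at each chamber visit, and precision may be lost on the cooling contrasts and the interaction whenever the true within-subject slope of final on starting temperature differs from 1. The omission creates neither a bias nor a demonstrated power shortfall.

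The plausible size runs from about a 1% variance loss, through cuts of about 6% to 22%, to 25% at the top of the equal-SD range. Every figure in that range rests on assumed values for the SD of the start and its relation to the end or to the change. The simulated cuts also assume a correlation of 0.5 between a subject's changes. The case for acting is that the possible loss is negligible and the possible gain is useful, above all if the correlation behind the within-group power is below 0.5.

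**What to change.** Before the data are analysed:
1. Define the starting temperature as the one pre-cooling value that is subtracted to form the elevation, and state whether it is the resting or the exercise-start reading.
2. Add one term to the Proc Mixed model: that visit's starting temperature minus the subject's mean starting temperature over the four chamber visits. State how the mean is formed if a visit is missing.
3. Leave the subject mean out of the primary model.
4. Report the unadjusted change-score model as a sensitivity analysis.

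The cost is a few sentences in the plan, one degree of freedom, and about 1% in variance if the covariate proves uninformative. No measurement, visit or subject is added.

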these individuals enjoy the rehabilitative and health benefits of physical activity and curtail adverse consequences of a sedentary lifestyle.

b. Current practice

N/A

3. Study Design.

Describe the study design (e.g., single/double blind, parallel, crossover, etc.) Consider inserting a scheme to visually present the study design.

We will conduct a randomized crossover design study. Non-burned control subjects, subjects who experienced burns covering ~20% to 40% of their body surface area, and subjects having burns >40% of their body surface area will be investigated. In one of the three environmental conditions outlined in Table 1, subjects will exercise while receiving one of the indicated cooling modalities.

Table 1: Proposed environmental conditions and cooling modalities.

Environmental Conditions	Condition A	Condition B	Condition C	Condition D
24 °C; 40% RH	Control (no fan or skin wetting)	Skin wetting only	Fan only	Skin wetting with a fan
30 °C; 40% RH	Control (no fan or skin wetting)	Skin wetting only	Fan only	Skin wetting with a fan
No higher than 40 °C; 40% RH	Control (no fan or skin wetting)	Skin wetting only	Fan only	Skin wetting with a fan

Table 2: Procedures and visits

	Visit 1	Visit 2	Visit 3	Visit 4	Visit 5
Informed Consent	X				
Urine Sample	X	X	X	X	X
Body Composition (DXA)	X				
Exercise Test	X				
12 lead ECG	X				
Alcohol Intake Survey	X				
International Physical Activity Survey	X				
Screening Questionnaire	X				
Heart Rate	X	X	X	X	X
Blood Pressure	X	X	X	X	X
Internal Temperature		X	X	X	X
Skin Temperature (including infrared imaging)		X	X	X	X
Skin blood flow and sweating measures		X	X	X	X
Blood samples		X	X	X	X

Form A

IRB # 30204 | STU-2020-0334

Metabolic Rate & ventilation		X	X	X	X
Perceptual Survey		X	X	X	X
Echocardiogram	X	X	X	X	X

4. Research Plan / Description of the Research Methods:

4.a. Provide a comprehensive narrative describing the research methods.

- 1) Provide the order in which tests/procedures will be performed,
- 2) Provide the setting for these events and a description of the methods used to protect privacy during the study.
- 3) Provide the plan for data analysis (include as applicable the sample size calculation)

Please respond to all components of this item, or clearly indicate which components are not applicable.

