The setting for all visits will be the Institute for Exercise and Environmental Medicine. Subjects will be recruited from: 1) the UTSW or IEEM volunteer research registry, 2) flyers/advertisements posted/shared at major burn centers throughout the United States, 3) info-articles and email blasts disseminated by our collaborator, the Phoenix Society, which is the largest burn support group in North America, as well as smaller (i.e., regional) burn support groups, 4) database of burned soldiers via our collaboration with the US Army, and 5) database of burn survivors maintained at UT Southwestern by the Co-Investigator ([name]) IRB protocol number: Study00000105. The latter database will be accessed by the Study Team to identify burn survivors who meet the inclusion/exclusion criteria outlined in Form C. Those individuals will be informed of the study, along with instructions to contact the Study Team should they be interested in participating.

Trials will be conducted in controlled laboratory settings. Burn survivors and non-burned individuals will perform bouts of exercise at a given environmental temperature as outlined in Table 1. Subjects will be required to perform exercise across all four of the conditions (i.e., Conditions A-D in Table 1) for a given environmental temperature. However, a subject will not be required to perform the battery of trials across all three environmental temperatures. Within a particular environmental temperature, the order of exposure for Conditions A-D will be randomized. Prior to being assigned to an order of cooling modalities for any given environmental temperature, we will obtain participant demographics, anthropometrics (body mass, height and composition) and aerobic capacity data.

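### The planned mixed model omits sex, although enrolment fixes it at 9 male and 9 female per group; adding it is a free but small gain for the between-group contrasts

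*Combined protocol and SAP*

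**What the plan says.** Section 3 defines three observed groups: "Non-burned control subjects, subjects who experienced burns covering ~20% to 40% of their body surface area, and subjects having burns >40" percent. Section 4.a randomises only the order of the cooling conditions.

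The statistical paragraph of section 4.a makes the group-by-condition interaction on the rise in internal temperature the primary evaluation within each environment. The model is a mixed one for repeated data, specified "with main factors of group and the applied cooling condition (crossover repeated factor), and their interaction, with subject modeled as a random effect". No covariate is named. Interactions are then explored through "least square means contrasts, applying Bonferroni type adjustments for multiple testing".

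The sample-size paragraph powers differences between groups, with a second figure "using an adjusted alpha of 0.0125 to account for multiple comparison evaluations of the four interventions between groups". It continues: "we will enroll 18 subjects per group (9 male and 9 female) for each environmental exposure", the increase over 12 being "to allow for attrition as well as provide additional power to evaluate any sex-related differences, should they become apparent". Neither paragraph gives a model term, contrast, test or trigger for that sex evaluation.

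**The concern.** Sex is controlled at enrolment and named as a possible subject of analysis, but it does not enter the only model given. Two things follow for the between-group contrasts within a condition, which are the comparisons the plan powers.

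- Any variance due to sex stays in their error term.
- The quota governs enrolment, not completion. The plan expects attrition, and if loss differs by sex across groups an unadjusted contrast can shift.

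The conditional sex evaluation also has no method. With no sex term, the stated analysis gives no way for a difference to become apparent. A decision to adjust made after an imbalance is seen would be data-driven.

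**Working it through.** **Inputs from the sample-size paragraph.** SD of the temperature rise about 0.3 °C; between-group difference 0.45 °C; 12 per group for power and 18 enrolled; alpha 0.05 and 0.0125. Sidedness is not stated; two-sided is assumed.

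**Assumed, because the documents give no sex effect.** Sex explains a share R² = 0.05 to 0.10 of the variance, with 0 as the null case. With equal numbers of each sex, a male-female difference D contributes D²/4 to the variance, so D = 2 × 0.3 × √R² = 0.134 to 0.190 °C.

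**1. Reproduce the stated power.** Pairwise contrast, 12 per group, error pooled over three groups (df = 33): SE = 0.3 × √(2/12) = 0.1225 and noncentrality = 0.45/0.1225 = 3.674. Power is 0.946 at alpha 0.05 and 0.842 at 0.0125, against the stated 0.94 and 0.84. The figures reproduce without a sex term. (An omnibus F test with equally spaced means over a 0.5 °C range fits equally well: 0.947 and 0.842.)

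**2. Add sex.** SE = 0.3 × √(1 − R²) × √(2/n); df = 3n − 3, less 1 when sex is fitted; half-width = t(0.975, df) × SE; power for 0.45 °C from the noncentral t at alpha 0.0125.

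| n per group | Model | df | SE (°C) | 95% half-width (°C) | Power |
|---|---|---|---|---|---|
| 18 | no sex | 51 | 0.1000 | 0.2008 | 0.969 |
| 18 | sex, R² = 0 | 50 | 0.1000 | 0.2009 | 0.969 |
| 18 | sex, R² = 0.05 | 50 | 0.0975 | 0.1958 | 0.976 |
| 18 | sex, R² = 0.10 | 50 | 0.0949 | 0.1905 | 0.982 |
| 12 | no sex | 33 | 0.1225 | 0.2492 | 0.842 |
| 12 | sex, R² = 0 | 32 | 0.1225 | 0.2495 | 0.840 |
| 12 | sex, R² = 0.05 | 32 | 0.1194 | 0.2432 | 0.861 |
| 12 | sex, R² = 0.10 | 32 | 0.1162 | 0.2367 | 0.882 |

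At a much larger assumed difference of 0.3 °C (R² = 0.3²/4/0.09 = 0.25), power would be 0.994 at 18 and 0.938 at 12.

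**3. What does not change.** Sex is constant within a subject, so an additive sex effect cancels from comparisons between conditions within subjects, and hence from the interaction in complete data. With 9/9 in every group it is also balanced across groups, so the group estimates do not move. A simulation (60 datasets per assumed sex difference, 18 per group, four conditions, REML, within-subject correlation 0.5 assumed) agreed: in complete data all these estimates changed by less than 1e-13. With 10% of visits missing at random, the largest change among the six interaction estimates averaged 0.005-0.007 °C, against an SE of 0.106-0.107 °C.

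**4. Unequal loss by sex.** Assume completers of 9 male/6 female in one group and 6/9 in another. The shift in the unadjusted contrast is the difference in male share times D: (9/15 − 6/15) × D = 0.2 × 0.134 to 0.2 × 0.190 = 0.027 to 0.038 °C. This applies if the subjects lost contribute no exercise visit. The planned mixed model keeps partial data. Generalised least squares with a random intercept, correlation 0.5 (assumed) and the same loss pattern gives:

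| Exercise visits from each subject lost | Shift (°C) |
|---|---|
| 0 | 0.027-0.038 |
| 1 | 0.009-0.013 |
| 2 | 0.004-0.006 |
| 3 | about 0.002 |

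An additive sex term removes the shift if the sex effect is itself additive.

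**5. What the sample can say about sex.** At SD 0.3 °C, alpha 0.05, one condition and no multiplicity adjustment, 27 versus 27 across groups has 80% power for a male-female difference of 0.23 °C. A sex-by-group difference between two groups needs 0.57 °C for 80% power, and has 60% power at 0.45 °C.

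**The case against.** The best defence is that little depends on this. The primary evaluation is the interaction, which an additive sex term leaves alone. Omitting a covariate that the design already balances is defensible, the gain rests on an assumed R², and it is only 0.005-0.010 °C of half-width at 18 per group. The sex evaluation is also conditional, so the plan does not promise one. All of this stands, and it sets the severity. It does not argue against the change, which costs almost nothing if sex has no effect.

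An additive term also tests only an average male-female difference. It cannot show whether the burn or cooling effects differ by sex. That is correct, and is why the fix has a second part.

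A reader might infer that the attrition shift is a bias of up to 0.038 °C. The documents give no attrition rate and no pattern by sex, and that figure needs opposite losses in two groups from subjects who complete no exercise visit.

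A reader might also infer that body mass confounds the group contrasts, since before the order is assigned "we will obtain participant demographics, anthropometrics (body mass, height and composition) and aerobic capacity data", while mass is analysed only descriptively and the exercise is described only as "Subjects will then exercise at a mild/moderate workload for 60 min". The documents do not support this. They show no mass gap between groups, so the size and direction of any effect are unknown. Adjustment is itself debatable, because mass may partly follow from burn-related inactivity.

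**Conclusion.** The model omits a factor that the design fixes and the sample-size paragraph names. The consequence is a modest loss of precision in the between-group contrasts within a condition. For an assumed R² of 0.05 to 0.10, adding sex narrows the half-width by 2.5 to 5% (0.1958/0.2008 = 0.975; 0.1905/0.2008 = 0.949) at 18 per group. At 12 per group it raises power by about 2 to 4 points. There is also some protection against loss that differs by sex: about 0.002-0.013 °C where those lost give one to three visits, and up to 0.038 °C where they give none.

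The documents do not support reading this as a bias in the primary analysis, an error in the power statement, or a broken promise to test sex. Severity is low. The sizes rest on the assumed sex effect, the SD of 0.3 °C and, for the partial-data shifts, the assumed correlation of 0.5.

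**What to change.** In the statistical paragraph of section 4.a, add sex as a fixed effect (1 df) to the mixed model. Add one sentence stating that sex-by-group and sex-by-condition terms will be fitted in a separate analysis labelled exploratory, so that the sex evaluation mentioned in the sample-size paragraph has a method.

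The cost is SAP wording only; sex is already known from the enrolment quota, and no visit, subject or procedure is added. If sex explains nothing, the price is about 0.0001 °C of half-width at 18 per group and about 0.1 point of power at 12 per group (0.8416 to 0.8402).

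### Condition order is blocked by a Latin square, but the primary mixed model has no period term, so any drift over Visits 2–5 costs precision and power for the group-by-condition interaction

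*Combined protocol and SAP*

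**What the plan says.** Item 3 declares a randomised crossover, and Table 2 there places the experimental measurements at Visits 2–5. Item 4.a, in the paragraph on trial conduct, requires every subject to complete all four conditions at a given environmental temperature and states: "Within a particular environmental temperature, the order of exposure for Conditions A-D will be randomized". The sample size paragraph adds: "Randomization within groups for the order of the applied cooling modality will be implemented with a Latin square blocking design".

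The data analysis paragraph of item 4.a says that, within each environmental exposure, "the primary evaluation will address an expected interactive effect of group and the employed cooling condition". The outcome is the rise in internal temperature over the 60-minute bout. The model is called two-factor, is to be fitted in SAS Proc Mixed, and has "main factors of group and the applied cooling condition (crossover repeated factor), and their interaction, with subject modeled as a random effect". A covariance structure is to be specified, but none is named. The post-hoc contrasts are taken from these models, and the mechanism variables (such as skin temperature) are handled in the same way.

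No section names a period, visit or sequence term.

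**The concern.** The design controls for visit order, but the analysis does not use that control. A Latin square makes order orthogonal, or nearly so, to condition. Leaving period out therefore does not bias the condition estimates on average over the randomisation. It does leave any mean shift between visits, for example from familiarisation or acclimation, in the within-subject residual. Choosing a covariance structure does not help: it describes scatter about the mean and cannot remove a change in the mean shared by all subjects at a visit.

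The error term is then too large. Standard errors are too wide, and tests of condition and of group by condition reject less often than their nominal level. What is at stake is lost power for the primary interaction, not false claims of a cooling effect.

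**Working it through.** **Inputs from item 4.a (sample size paragraph).** SD of the rise 0.3 °C; 12 per group for power, 18 enrolled; alpha 0.05 and 0.0125; differences of 0.45 °C between groups and 0.4 °C within group.

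**Assumptions not in the documents.** Within-subject correlation 0.5 (range 0.3 to 0.7); linear drift of d °C per visit, common to all groups; complete data; compound symmetry.

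**The plan's own figures.** A two-sided two-sample t-test with 12 per group and 0.45/0.3 = 1.5 SD gives power 0.939 at alpha 0.05 (stated 0.94) and 0.819 at 0.0125 (stated 0.84). A three-group ANOVA with means 0, 0.25 and 0.5 °C, the spread named first in that paragraph, gives 0.947 and 0.842. For the claim "For the within group comparison, power is >0.9 to detect a difference in the increase in internal body temperature of 0.4 °C" at alpha 0.0125, a paired t-test with n = 12 gives 0.767 at correlation 0.25 and 0.925 at 0.5. The stated figure is therefore consistent with a correlation of about 0.5. None of these figures is for the interaction.

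**Closed form for a complete square.** Within-subject variance is 0.3² × (1 − 0.5) = 0.045. With 18 per group, the SE of a within-group cooling contrast is √(2 × 0.045/18) = 0.071. Over four visits the drift deviates from its mean by −1.5d, −0.5d, 0.5d and 1.5d, with sum of squares 5d². Spread over 3 within-subject degrees of freedom, this adds 5d²/3 to the residual variance. The true sampling variance of the contrast does not change; only its estimate is inflated.

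| d (°C per visit) | 5d²/3 | Residual variance | SE ratio | Reported SE |
|---|---|---|---|---|
| 0 | 0 | 0.0450 | 1 | 0.071 |
| 0.05 | 0.0042 | 0.0492 | √(0.0492/0.045) = 1.045 | 0.074 |
| 0.10 | 0.0167 | 0.0617 | √(0.0617/0.045) = 1.17 | 0.083 |

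With period in the model, the SE stays at 0.071 throughout.

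**Simulation of the primary test.** Three groups of 18 and 4,000 trials per setting. Each group uses Latin square sequences, with the two surplus sequences drawn at random. The test is the 6-df interaction F test at 0.05. Entries are without / with period; the effect sits in one group-by-condition cell.

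| d | Type I error | Power, 0.2 °C | Power, 0.3 °C | Power, 0.4 °C |
|---|---|---|---|---|
| 0.05 | 0.032 / 0.047 | 0.45 / 0.52 | 0.86 / 0.90 | 0.99 / 1.00 |
| 0.10 | 0.009 / 0.047 | 0.27 / 0.52 | 0.73 / 0.90 | 0.97 / 1.00 |

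With no drift, power for 0.2 °C is 0.516 / 0.517. At d = 0.025 it is about 0.49 without and 0.50 to 0.52 with period, close to simulation error. At d = 0.05, the 0.2 °C figures are 0.31 / 0.36 for correlation 0.3 and 0.67 / 0.77 for correlation 0.7.

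**Stated within-group power (0.4 °C, alpha 0.0125) at d = 0.10.** 0.997 / 1.000 with 18 per group and 0.94 / 0.98 with 12, using the pooled model error. The plan's >0.9 holds either way.

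**Incomplete squares.** 18 is not a multiple of 4, so the best split over four sequences is 5/5/4/4. Per 0.10 °C of drift per visit, a Williams square then shifts fan-plus-wetting minus control by 0, 0.006 or 0.017 °C, depending on which two sequences are surplus. A cyclic square shifts it by 0.011 °C for every pair. The plan does not say which square is used. These shifts average to zero over the randomisation.

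**The case against.** The strongest objection is that the loss depends entirely on a drift that the documents neither state nor suggest. The outcome is a within-session rise at a mild to moderate workload in a controlled chamber, so day-to-day changes in baseline temperature are already subtracted. A drift of 0.10 °C per visit is 3 × 0.10 = 0.30 °C over Visits 2–5, a full SD of the outcome. That is fair: 0.10 is an upper-end scenario, and at 0.025 the loss is negligible.

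Second, no stated claim of the plan fails. At d = 0.05 and correlation 0.5, a power loss above 5 points appears only for the 0.2 °C cell effect, which is half the 0.4 °C difference planned within groups. This also stands. But the plan sets no target for the interaction, so it cannot show that its primary test has power to spare.

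Third, complete data were assumed although the plan expects attrition. If 30% of subjects stop early (an assumption), the type I error without period is 0.041 at d = 0.05 and 0.024 at d = 0.10, so the test is less conservative than tabulated. Imbalance then lets drift into the estimates as well as the residual. The gain from the period term remains: power for 0.2 °C is 0.35 without and 0.41 with period at d = 0.05, and 0.24 against 0.42 at d = 0.10.

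These points limit the size of the concern. None supplies the missing term or gives a reason to leave it out.

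**Conclusion.** The concern holds. The primary model omits the factor on which the randomisation is blocked, and nothing elsewhere in the document supplies it. The consequence is conservative tests and lost power, with no average bias and no added false-positive risk. Under the stated assumptions the loss for a 0.2 °C cell effect is about 7 points of power at 0.05 °C drift per visit (0.52 − 0.45) and 25 points at 0.10 (0.52 − 0.27). It is close to nothing at 0.025 or below.

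Two limits apply. The figures rest on an assumed drift and correlation. And if drift differs between groups, a common period term restores the test size only partly. With a total drift of 0.2 °C over the four visits plus a further 0.3 °C in one group, type I error at 18 per group was 0.011 without period and 0.039 with it. Carryover is a separate matter and was not examined.

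The change should be made because it is almost free. It does not decide whether the trial can reach a valid conclusion.

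**What to change.** Add period as a categorical fixed effect (four levels, 3 degrees of freedom) to the Proc Mixed model for internal temperature and to the models for the mechanism variables, so that the post-hoc least-squares-means contrasts are adjusted as well. Define period as the order of the exercise visits within the given environmental exposure, because the plan does not bar a subject from completing more than one exposure.

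The cost is one model term. With 18 per group there are 54 × 3 = 162 within-subject degrees of freedom. Condition (3) and interaction (6) leave 153 for error, and period reduces this to 150. With no drift there is no material loss of power (0.516 without, 0.517 with). Design, conduct and sample size do not change.
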